## List of Abbreviations

|                    |   |
|--------------------|---|
| AE                 | Adverse Event                             |
| ALT                | Alanine Aminotransferase                  |
| ANOVA              | Analysis of Variance                      |
| aPTT               | Activated Partial Thromboplastin Time     |
| AST                | Aspartate Aminotransferase                |
| ATC                | Anatomical Therapeutic Chemical           |
| BDRM               | Blind Data Review Meeting                 |
| CI                 | Confidence Interval                       |
| CSP                | Clinical Study Protocol                   |
| CSR                | Clinical Study Report                     |
| DRM                | Data Review Meeting                       |
| eCRF               | Electronic Case Report Form               |
| ELISA              | Enzyme Linked Immunosorbent Assay         |
| GMFI               | Geometric Mean Fold Increase              |
| GMT                | Geometric Mean Titer                      |
| HIV                | Human Immunodeficiency Virus              |
| IMP                | Investigational Medicinal Product         |
| IMP                | Investigational Medical Product           |
| LLOQ               | Lower Limit of Quantification             |
| MITT               | Modified Intent-to-Treat                  |
| PP                 | Per-Protocol                              |
| PRNT 50 | Plaque Reduction Neutralization Test 50 % |
| PT                 | Prothrombin Time                          |
| SOP                | Standard Operating Procedure              |
| SPS®               | Stabilizing and Protecting Solutions      |
| TLF                | Tables Listings and Figures               |
| ULOQ               | Upper Limit of Quantification             |
| VNT                | Virus Neutralization Test                 |

## 1. OVERVIEW

### 1.1 Study Objectives

#### 1.1.1 Primary Objective

- To investigate safety and tolerability of MV-ZIKA-RSP, a novel liquid vaccine formulation, up to day 56 after first immunization consisting in one or two vaccinations

Safety and tolerability will be assessed by the rate adverse events (AEs) after the first vaccination up to day 56.

#### 1.1.2 Secondary Objectives

- To investigate long-term safety, up to study day 182, after first immunization

Long term safety and tolerability will be assessed by means of a phone call where participants will be asked about any adverse event (solicited, unsolicited or serious adverse event) experimented after the Visit 3 (day 56)

- To investigate immunogenicity up to day 56 after first immunization consisting in one or two vaccinations with different doses

To cover this objective the presence of functional anti-zika antibodies will be determined by means VNT and ELISA at the following time points: Visit 1 (day 0), Visit 2 (day 28) and Visit 3 (day 56) after first vaccination

- To get information about the optimal dose of MV-ZIKA-RSP vaccine regarding safety, tolerability and immunogenicity

An evaluation of the optimal dose will be determined after analysis of the safety, tolerability and immunogenicity (VNT)

- To investigate specific cell mediated immunity induced by all different treatment groups

Cell mediated immunity up to day 56 will be assessed by T cell analysis of PBMC isolated on study days 0, 28 and 56

### 1.2 Study Design

This is an observer-blinded, block-randomised, dose finding, phase I trial, comparing different dose levels of MV-ZIKA-RSP to evaluate safety, tolerability and immunogenicity, of this novel ZIKA-RSP vaccine. Placebo (physiological saline solution) will be applied to blind the different treatment schedules.

The study will be conducted at a single study site, Medical University Vienna.

After the screening procedures, 48 healthy male and female volunteers aged 18-55 years will be randomly assigned to one of four treatment groups (A, B, C or D). Participants will be assessed for immunogenicity on days 0, 28 and 56 (treatment period), as confirmed by the presence of functional anti-zika-rsp antibodies determined by (VNT) and

by ELISA, at the same time safety will be also assessed. After the treatment period, participants will be call by phone (day 182) for evaluation of safety follow-up.

Study duration per subject will be 182 days (6 months), consisting of 4 weeks treatment period (study day 0 till study day 28) and 22 weeks follow up period (study day 2 till study day 182)

### 1.3 Endpoints

#### 1.3.1 *Primary Endpoint*

- Rate of adverse events (AEs) up to study day 56

#### 1.3.2 *Secondary Endpoints*

[figure not shown]
- Rate of solicited and unsolicited AEs, as well as, reported serious adverse events (SAEs) up to study day 182 (long-term safety) compared between the 4 different treatment groups.
- Immunogenicity on study days up to study day 56 as confirmed by the presence of functional anti-zika antibodies as determined by VNT and by ELISA
- Cell-mediated immunity specific for ZIKA-RSP, up to study day 56, confirmed by the presence of specific functional CD4+ and CD8+ T-cells
- Safety laboratory parameters (haematology, serum chemistry, urinalysis)

### 1.4 Sample Size Calculation

A formal sample size calculation was not conducted. The sample size of 48 participants has been determined based on prior experience in evaluating the safety and immunogenicity of vaccines and is typical for early phase clinical studies. Sample size for this study was determined on grounds of feasibility and common practice in similar trials.

## 1.5 Study Flowchart and Study Procedures

Study flowchart:

Study procedures:

|                                       | Screening | Treatment |                     |            |                     | Post Treatment Safety Follow Up | ET     |
|---------------------------------------|-----------|-----------|---------------------|------------|---------------------|---------------------------------|--------|
| Visit                                 | VS        | V1        | Post dose safety FU | V2         | V3 Primary Endpoint | V4                              | (1)    |
| Study Day                             | -14 to -1 | 0         |                     | $28 \pm 3$ | $56 \pm 3$          | $182 \pm 14$                    |        |
| Informed Consent                      | x         |           |                     |            |                     |                                 |        |
| Inclusion/Exclusion Criteria          | x         | x         |                     |            |                     |                                 |        |
| Medical History                       | x         | x         |                     |            |                     |                                 |        |
| Vaccination History                   | x         | x         |                     |            |                     |                                 |        |
| Vital Signs (2)                       | x         | x         |                     | x          | x                   |                                 | x      |
| Symptom-directed Physical Examination |           | x         |                     | x          | x                   |                                 | x      |
| System-based Physical Examination (6) | x         | x         |                     | x          | x                   |                                 | x      |
| Adverse Events (3) (7)                |           | x         | x                   | x          | x                   | x                               | x      |
| Prior/Concomitant Medication (4)      | x         | x         | x                   | x          | x                   | x                               | x      |
| Clinical Laboratory (5)               | x         |           |                     | x          | x                   |                                 | x      |
| Randomization                         |           | x         |                     |            |                     |                                 |        |
| Urine Pregnancy Test (12)             | x         | x         |                     | x          | x                   |                                 | x      |
| Study Treatment                       |           | x         |                     | x          |                     |                                 |        |
| Immunogenicity (VNT) (12)             |           | x         |                     | x          | x                   |                                 | x      |
| T-cell immunity (PBMCs) (12)          |           | x         |                     | x          | x                   |                                 | x (11) |
| Zika antibody (ELISA) (12)            |           | x         |                     | x          | x                   |                                 | x      |
| Measles antibody (ELISA) (12)         |           | x         |                     | x          | x                   |                                 | x      |
| Local Tolerability (7)                |           | x         |                     | x          | x                   |                                 | x      |
| Dispense subject diary                |           | x         |                     | x          |                     |                                 |        |

Adapted from:

STAT03\_A Statistical Analysis Plan

Version 6.0, Effective Date 16-Feb-2018

Page 8 of 33

Confidential and intellectual property of Assign DMB. No part of this document or its contents may be duplicated, referenced, published or otherwise disclosed in any form or by any means without prior written consent of Assign DMB.

|                                  |  |  |       |   |   |        |   |
|----------------------------------|--|--|-------|---|---|--------|---|
| Collect and review subject diary |  |  |       | x | x |        | x |
| Safety phone call (9)            |  |  | x (9) |   |   | x (10) |   |

- (1) Early termination visit should – if possible - be conducted 28±3 days after last IMP administration.
- (2) Systolic/diastolic blood pressure, pulse rate, body temperature
- (3) Conditions/symptoms noted prior to randomization should not be reported as AE, but should be reported as medical history
- (4) Medications administered up to 30 days prior to screening until end of study participation should be documented
- (5) The clinical laboratory comprises: Hematology (hemoglobin, hematocrit, erythrocyte count, differential white blood count, platelets), Chemistry (creatinine, potassium, sodium, calcium, AST, ALT, alkaline phosphatase, bilirubin), Coagulation (prothrombin time (PT), activated partial thromboplastin time (aPTT), fibrinogen), Urinalysis (standard urine test stick for determining pH-value, glucose, protein, bilirubin, urobilinogen, red blood cells, white blood cells, nitrite, ketone and specific gravity), Virology (only at screening; HBs-Ag, anti-HBc-Ab, anti-HCV-Ab, HIV 1/2 Ab/HIV-1 Antigens if not done within 30 days before screening)
- (6) To be performed if necessary, according to findings in symptom-directed physical examination
- (7) To be performed 1 hour after each IMP administration and additionally at the subsequent visit (prior to IMP administration, if applicable)
- (8) Participants should be interviewed regarding potential AEs since the last study visit. If indicated, participants should be called in for an unscheduled visit.
- (9) The post dose safety call follows up should be conducted 7±1 days (one week) after the first vaccination.
- (10) The post treatment safety call follows up should be conducted 182 days (6 months) after the first study treatment also in case of an early termination.
- (11) The amount of blood sample taken during the early termination (ET) visit depends on the time point of the visit. If the ET-visit replaces the primary endpoint visit on day 56±3, 48 to 60 mL blood should be taken; otherwise 24 to 48 mL are enough.
- (12) Urine for pregnancy test should be taken before vaccination

## 2. GENERAL CONSIDERATIONS

### 2.1 Conduct of Analysis

A preliminary analysis including safety and immunogenicity data will be performed after all participants completed Visit 3 (day 56) and therefore terminated the treatment period of the study. This analysis will cover the primary safety endpoint (adverse events up to day 56) and some immunogenicity endpoints. The purpose of this analysis is to provide highly valuable data for further zika vaccine development.

Results from this preliminary analysis will not have any impact on the study design or the participants during the follow up period of the study.

The final analysis will be conducted after the last subject completed the Post Treatment Safety Follow-Up and the database was closed. All data of the study will already be available at the preliminary analysis except the Adverse Events and Prior/Concomitant Medication data from Visit 4 (Day 182). Thus, only Adverse Events and Prior/Concomitant Medication data will be analyzed at the final analysis. If unexpected changes occur e.g. in the immunogenicity data, analyses may also be repeated at the final analysis.

SAP update (Final 2.0): Due to the covid pandemic, at the time of analysis of the samples, laboratory capacities were limited, and no results were available. For this reason, immunogenicity analysis was not conducted for the preliminary analysis. Instead, the immunogenicity analysis will be done as described in Section 5 for the final analysis only.

### 2.2 Statistical Software and Quality Control

All statistical analyses will be performed using SAS® version 9.3 or higher. Tables, figures and data listings will be generated in Microsoft® Word® as well as PDF® format.

Quality control of SAS® programs will include a review of the whole process of result generation:

- Review of all analysis SAS® programs
- Review of SAS® log for errors, warnings and other notes that could indicate mistakes in the programs
- Review of all tables, listings and figures for completeness and correctness

### 2.3 Applicable Standard Operation Procedures

The applicable Standard Operating Procedures (SOPs) of Assign DMB for this study are:

- STAT01 Statistical Analysis File
- STAT03 Statistical Analysis Plan
- STAT04 Interim Analysis
- STAT05 Randomization and Unblinding
- STAT06 Data Review Meeting

- STAT07 Report Writing
- SAS01 SAS General Principles
- SAS04 Handling of Statistical Analyses

## 2.4 Blinding and Randomization

### Blinding:

As this study will be conducted in an observer-blinded manner, unblinded study team members responsible for randomisation, monitoring (unblinded monitor) and preparation of IMP, will otherwise not be involved in the conduct of the study.

All participants, the investigator and site personnel performing study related assessments, as well as the sponsor's representatives involved in the monitoring (blinded monitor) and conduct of the study, will be blinded to treatment assignment.

Besides one set of randomisation envelopes, the site will receive an additional set of emergency envelopes stored in the ISF for unblinding purposes. As the knowledge of the subject's treatment might become mandatory (e.g. in case of emergency) the investigator has the possibility to open the emergency envelope, identified with the subject's randomisation number, and unblind the subject.

The investigator and site personnel assessing AEs, all participants, as well as one of the sponsor's representatives involved in the monitoring and conduct of the study will be blinded to which vaccine was administered. Only the unblinded monitor, site personnel performing randomisation and preparation of IMP will be unblinded.

The primary endpoint as well as most of the secondary endpoints will be covered in the preliminary analysis after Day 56 and only a safety follow-up phone call will be performed after Day 56. The sponsor personnel and ADMB team, involved in generation and review of the preliminary analysis and underlying data management activities, will be unblinded after the Blind Data Review Meeting (Section 2.9) and database snapshot for preliminary analysis.

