### **8.3 Blinding and Code-breaking**

As this study will be conducted in an observer-blinded manner, unblinded study team members responsible for randomisation, monitoring (unblinded monitor) and preparation of IMP, will otherwise not be involved in the conduct of the study.

All participants, the investigator and site personnel performing study related assessments, as well as the sponsor's representatives involved in the monitoring (blinded monitor) and conduct of the study, will be blinded to treatment assignment.

Besides one set of randomisation envelopes, the site will receive an additional set of emergency envelopes stored in the ISF for unblinding purposes. As the knowledge of the subject's treatment might become mandatory (e.g. in case of emergency) the investigator has the possibility to open the emergency envelope identified with the subject's randomisation number and unblind the subject.

Please note that this code-breaking should only be done by the investigator if the knowledge of the subject's treatment influences the decision on further procedures. If unblinding would not make any difference for further treatment, the study team should remain blinded.

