#### 10.1.3 Adverse Reaction (AR)

An untoward and unintended response in a participant to an investigational medicinal product which is at least possibly related to any dose administered to that participant.

All cases judged by either the reporting medically qualified professional or the sponsor as having a reasonable suspected causal relationship to the trial medication qualify as adverse reactions.

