## 2.12 Subject Data Listings

All treated subjects will be included in listings if not stated otherwise (e.g. subject overview listings, screening failure listing). Data listings will include the subject number as identifier (and parameter and/or visit if available) and will be sorted by treatment group, subject number and parameter and/or visit if available (in this order). Columns that indicate the treatment group will be shown in all listings.

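### The Day 56 unblinding includes data-management staff while AEs to Day 182 are still to be queried, and no blind is described for that work or for a second data review meeting

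*Combined protocol and SAP*

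**What the plan says.** SAP 2.4 sets the rule for the preliminary analysis: "The sponsor personnel and ADMB team, involved in generation and review of the preliminary analysis and underlying data management activities, will be unblinded". The same sentence gives the timing; these people "will be unblinded after the Blind Data Review Meeting (Section 2.9) and database snapshot for preliminary analysis". The group includes those who do the data management behind the analysis as well as those who program and review it. Access is at participant level, because under SAP 2.12 "Columns that indicate the treatment group will be shown in all listings".

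The AE data are incomplete at that moment. SAP 2.1 expects all study data to be available at the preliminary analysis "except the Adverse Events and Prior/Concomitant Medication data from Visit 4 (Day 182". (A later update moves immunogenicity to the final analysis as well; this point concerns AEs only.) AE rates to Day 182, compared across the four groups, are a secondary endpoint (protocol 6.2.2, SAP 1.3.2). SAP 2.6 applies the same overall test to the AE tables at Day 56 and at the end.

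Other text describes the blind differently:
- Protocol 8.3 says that the sponsor's "representatives involved in the monitoring (blinded monitor) and conduct of the study, will be blinded to treatment assignment", with no end date.
- Protocol 6.1 and an earlier paragraph of SAP 2.4 list those kept blind: "The investigator and site personnel assessing AEs, all participants, as well as one of the sponsor's representatives". They name only the unblinded monitor and the site staff who randomise and prepare product as unblinded.
- Protocol 12.5.3 and SAP 2.11.3 refer to unblinding of the study at the preliminary analysis, without saying for whom.
- SAP 2.9 makes the first data review meeting blind. It allows a second one before database closure, to discuss which analyses may be repeated, and does not call that one blind.

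**The concern.** The CRO whose team is unblinded also maintains the eCRF and study database (protocol 15.4.1). Computerised and manual checks raise queries to the site (protocol 15.4.2). Neither document describes a separate blinded query or coding team for the period after the snapshot, or a barrier between unblinded staff and the site.

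Someone who knows the arm may, without intending to, pursue a missing or doubtful AE entry harder in one group than in another. At stake is the between-group comparison of AEs in the final tables, chiefly the rows for related and severe events. A second review meeting held with treatment known could also let the results influence which analyses are repeated.

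**Working it through.** The plan gives no figure for this exposure, so there is none to reproduce. Its design figures agree with each other: 14 + 14 + 12 + 8 = 48 participants, and 4 + 22 weeks = 26 weeks = 182 days.

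**1. Who can affect a post-Day 56 AE record**
- Eliciting, grading and attributing: the investigator and site staff (protocol 8.6.1, 10.2), who stay blinded.
- Entering and correcting data: only the investigator or authorised site staff, with an audit trail (protocol 15.4.1).
- Raising queries: monitors and data checks (protocol 15.4.2). Database maintenance is with the CRO, whose data-management staff for the preliminary analysis are unblinded by SAP 2.4.
- MedDRA coding: SAP 2.10 names no coder and gives no blinding status.
- Second data review meeting: attendees and blinding status not stated (SAP 2.9).

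**2. How a query can reach a table**
- Missing causality is taken as definitely related (SAP 2.8) and counts as related (SAP 6.2.2). If a query is answered as unlikely or not related, the event leaves the related rows.
- Missing severity is taken as potentially life threatening and enters the severe rows (SAP 2.8, 6.2.2). An answer of mild or moderate removes it.
- An AE with missing solicited/unsolicited status is in neither of those sets of tables, only in the all-AE tables (SAP 2.8). An answer puts it into one of them.

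So whether a query is raised and pursued can change a count, even though a blinded person answers it. The documents do not say how many AEs would have such gaps.

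**3. Share of follow-up after the cut-off**

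Inputs: Visit 3 at day 56 ± 3 and Visit 4 at day 182 ± 14.
- Nominal: (182 − 56)/182 = 126/182 = 69.2%.
- Shortest within windows: (168 − 59)/168 = 64.9%. Longest: (196 − 53)/196 = 73.0%.

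The snapshot follows the last participant's Visit 3, so earlier enrolees have less time still to run. Enrolment length and the lag to the snapshot are not given. Assume uniform enrolment over E days and a lag of L days. The share still to come is then the average of max(0, 126 − L − e)/182 over e from 0 to E:

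| E (days) | L = 0 | L = 30 |
|---|---|---|
| 0 | 69% | 53% |
| 60 | 53% | 36% |
| 126 | 35% | 20% |
| 180 | 24% | 14% |

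For example, E = 60 and L = 0 gives (126 − 30)/182 = 96/182 = 53%. These are shares of calendar time, not of events or records. A participant whose Visit 4 call is still pending may report earlier events in that call.

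**4. Weight of one participant**

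Percentages use the group total (SAP 6.2.2): 1/14 = 7.1 points in A or B, 1/12 = 8.3 in C, 1/8 = 12.5 in D. The shift occurs only if the event is the participant's sole qualifying one, because the final tables cover all AEs from the first vaccination. In the predecessor trial 75.0% reported solicited and 81.3% unsolicited AEs, so many later events would not change an any-AE row. Drug-related events were reported by 37.5%, which leaves more room for change in the related rows.

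**The case against.** The strongest reply is that this is a disclosed choice with little left to bias. SAP 2.4 gives its reason in the same paragraph: the primary and most secondary endpoints are covered by then, and one phone call remains. Protocol 12.5.3 foresees unblinding at the preliminary analysis, so protocol 8.3 should not be read alone. Protocol 12.1 says that the results will not affect the design or the participants. SAP 2.3 lists CRO procedures on interim analysis and on unblinding, which may contain access controls that a reader of the SAP cannot see. All of this stands, and it keeps the point small. It does not tell the reader who handles queries after Day 56, or whether they know the arms.

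A reader might infer more than the documents support:
- That late AEs are assessed unblinded. They are not: the investigator, site assessors and participants remain blinded.
- That sponsor causality can move the tables, since protocol 10.1.3 counts "All cases judged by either the reporting medically qualified professional or the sponsor as having a reasonable suspected causal relationship" as adverse reactions. SAP 6.2.2 derives related events from the recorded relationship, which only site staff may edit, and the AE listings carry one relationship field. The protocol definition also lets the sponsor add a suspected relationship but not remove one.
- That unblinded staff do the coding. This is possible but not stated.
- That all by-arm participant listings should be withheld from sponsor reviewers. In a first-in-human trial, reading individual events by dose may be what the review is for, so this is a trade-off and not part of the point.

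**Conclusion.** The point holds in a limited form. SAP 2.4 gives data-management staff knowledge of individual arms while AEs to Day 182 are still to be queried and compared. No blind is described for querying, coding or a second review meeting. The documents do not support a claim that the long-term safety comparison as a whole is handled unblinded.

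The primary endpoint, "Rate of adverse events (AEs) up to study day 56", is analysed from a snapshot taken before this unblinding. What is exposed is the secondary AE comparison to Day 182, through queries and possibly coding. The 69% is a nominal per-participant ceiling on time, and 7.1 to 12.5 points is the most that one participant can shift a group rate. Neither figure estimates bias. The conclusion assumes that at least some of the unblinded data-management staff go on to handle later AE data. The SAP neither says so nor rules it out. This is a small phase I trial with no formal sample-size calculation, so the case for a change rests mainly on its low cost.

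**What to change.** In SAP 2.4:
- Limit unblinding at the Day 56 snapshot to the statisticians and programmers who produce the preliminary tables, and to named sponsor reviewers with no role in AE querying, coding or monitoring.
- State that data managers, coders, the blinded monitor and everyone attending a second data review meeting stay blinded until final database closure.
- Bar the transfer of participant-level treatment information to the site. Emergency code-breaking and SUSAR unblinding stay as they are.
- Reconcile this text with protocol 8.3, and say in protocol 12.5.3 and SAP 2.11.3 who is unblinded at the preliminary analysis.

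If the unblinding has already taken place, record in the SAP and the clinical study report who was unblinded, when, and what part they later had in handling AE data.

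The cost is SAP wording and restricted access to treatment codes, with no extra staff expected. Data-handling staff see the codes only after final closure, and any second review meeting must draw on people outside the unblinded group. Named sponsor reviewers can still read participant listings by arm.
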